7.3.3 Serious Adverse Events

A "serious" adverse event is defined in regulatory terminology as any untoward medical occurrence that:

7.3.3.1 Results in death.

If death results from (progression of) the disease, the disease should be reported as event (SAE) itself.

7.3.3.2 Is life-threatening.

(the patient was at risk of death at the time of the event; it does not refer to an event that hypothetically might have caused death if it were more severe).

7.3.3.3 Requires in-patient hospitalization or prolongation of existing hospitalization for \geq 24 hours.

Following events do not satisy criteria for SAE: Hospitalizations for preplanned procedures Hospitalization for study-related treatment and procedures

- **7.3.3.4** Results in persistent or significant disability or incapacity.
- **7.3.3.5** Is a congenital anomaly/birth defect
- 7.3.3.6 Is an important medical event

Any event that does not meet the above criteria, but that in the judgment of the investigator jeopardizes the patient, may be considered for reporting as a serious adverse event. The event may require medical or surgical intervention to prevent one of the outcomes listed in the definition of "Serious Adverse Event". For example: allergic bronchospasm requiring intensive treatment in an emergency room or at home; convulsions that may not result in hospitalization; development of drug abuse or drug dependency.

7.4 Reporting Requirements

Adverse events, serious adverse events, deviations, violations, and unanticipated problems must be entered into the clinical trial management system (CTMS), OnCore, and must also be reported to the following entities according to the timelines mentioned in the chart below. Serious adverse events collection will start at the time patient signs consent until 30 days after the end of treatment. Adverse events will be collected from the time the research patient begins treatment until 30 days after the end of treatment. All adverse events/serious adverse events should be followed until resolution or stabilization.

Event Type	Coordinating Center/Medical Monitor	UCI IRB	Exelixis, Inc.	CFCCC DSMB
Unanticipated Problem	Within 24 hours from date the site is aware of the event, the site should enter this information into OnCore. An email notification should also be sent via email to [contact] and [contact] .	Within 5 business days submit an Unanticipated Problem Report (UP). Current policy can be found here.	Within 1 business day of learning of the event. Submit a MedWatch Form to Exelixis via [contact]) or email ([contact]). All follow up information must be sent to Exelixis within 1 business day of PI's receipt of new information. Please refer to section 7.6 for further information.	Within 5 days from date PI is aware of the event. This information must be reported into OnCore.
AEs and SAEs (non- Unanticipated Problem)	Please refer to section 7.5 for reporting timeframes on AEs and SAEs	N/A	Please refer to section 7.6 for other reportable events	Please refer to section 7.5 for clarification on reporting timeframes for AEs and SAEs
Non-compliance	N/A	N/A	N/A	Please refer to section 7.5 for reportable deviations/violations
Serious or continuing non-compliance	Within 24 hours via email to [contact] and [contact]	Within 5 business days submit a New Information Report	N/A	Within 5 days from date PI is aware of the event.
Prospective/Planned Deviations	At least 5 business days prior to the event via email to [contact] and [contact] for approval.	At least 48 hours prior to date the request is needed by. Submit a Prospective Deviation Request form	N/A	At the time of progress review as aggregate reports

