2.3 Endpoints

The primary endpoint is 6 months progression-free survival (PFS-6). The secondary endpoints are rates of drug-related grade 3-5 adverse events experienced during and up to four weeks after completion of study treatment. These will be assessed via NCI's CTCAE v5.0 toxicity criteria. Other secondary endpoints are best objective response rate by RECIST v1.1 in patients with measurable disease and overall survival.

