- Any non-protocol systemic anticancer treatment (e.g., chemotherapy, immunotherapy, radionuclides, drugs or herbal products used specifically for the treatment of the cancer under investigation).

- Immunosuppressive agents including immunosuppressive doses of systemic corticosteroids with exceptions as stated in Section 4.1.2.1.
- Live vaccines are prohibited while on study and until 5 months after last dose of IO
 agent (e.g., intranasal influenza, measles, mumps, rubella, oral polio, BCG, yellow
 fever, varicella, and TY21a typhoid vaccines). The use of inactivated (killed)
 vaccines for the prevention of infectious disease is permitted.
- Metamizole (dipyrone) because of its potential for causing agranulocytosis.

The following therapies should be avoided until study treatment has been permanently discontinued or until otherwise specified:

- Local anticancer treatment including palliative radiation, ablation, embolization, or surgery with impact on tumor lesions should not be performed until radiographic progression per RECIST 1.1 has been established.
- Erythropoietic stimulating agents (e.g., epoetin alfa and darbepoetin alfa) should not be used based on a report of increased risk of tumor recurrence/progression associated with erythropoietin (Wright et al 2007).
- Concomitant medications that are known to prolong the QTc interval should be avoided in subjects who receive cabozantinib until they have permanently discontinued cabozantinib treatment (refer to http://www.qtdrugs.org for a list of drugs which have the potential to prolong the QTc interval).
- Chronic co-administration of cabozantinib with strong inducers of the CYP3A4 family (e.g., phenytoin, carbamazepine, rifampin, rifabutin, rifapentine, phenobarbital, and St. John's Wort) may significantly decrease cabozantinib concentrations and should be avoided. Selection of alternate concomitant medications with no or minimal CYP3A4 enzyme induction potential is recommended.
- Caution must be used when discontinuing treatment with a strong CYP3A4 inducer in a subject who has been concurrently receiving a stable dose of cabozantinib, as this could significantly increase the exposure to cabozantinib.

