5.3.2 Within 30 days after treatment termination

- · Physical exam, vital signs
- Hematology
- Serum chemistries
- Adverse events
- · Review previous and concomitant medications
- Pregnancy Test (if applicable)

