5.4 Follow-up Procedures

Patients will be followed every three months after completion of (or early withdrawal from) study treatment until death or up to 18 months after the last patient is enrolled, whichever comes first.

• Review of systems and determination of live status (either in clinic during standard visit or by phone)

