Infusion-related reactions: Infusion-related reactions (including severe and life-threatening cases) have occurred. Monitor for signs/symptoms of a reaction (eg, rigors, chills, wheezing, pruritus, flushing, rash, hypotension, hypoxemia, and fever). Interrupt infusion and permanently discontinue for severe (grade 3) or life-threatening (grade 4) infusion-related reactions.

Nephrotoxicity: Immune-mediated nephritis has occurred. The onset for autoimmune nephritis was 3.2 to 5.1 months (range: 12 days to 12.8 months) and the median duration was 3.3 months (range: 12 days to over 16 months). Grade 2 or higher nephritis should be managed with systemic corticosteroids (prednisone initial dose of 1 to 2 mg/kg/day [or equivalent], followed by a taper). Most patients required systemic corticosteroids. The median duration of corticosteroid use was 3 to 15 days (range: 1 day to 4 months), followed by a taper. Nephritis resolved in approximately one-third to one-half of affected patients. Monitor for renal function changes. May require treatment interruption, systemic corticosteroids (for grade 2 or higher toxicity), and/or permanent discontinuation.

Pulmonary toxicity: Immune-mediated pneumonitis has been observed, including grade 3, grade 4, and fatal cases. In patients with NSCLC, a higher incidence of pneumonitis was reported in patients who had received prior

thoracic radiation. The median time to development was 3.3 months (range: 2 days to ~19 months) and the median duration was 1.5 months (range: 1 day to over 17 months). Many patients required initial management with high-dose systemic corticosteroids; the median duration of initial corticosteroid therapy was 5 to 8 days (range: 1 day to ~10 months) followed by a corticosteroid taper. Pneumonitis resolved in half of the affected patients. May require treatment interruption, corticosteroid therapy (prednisone 1 to 2 mg/kg /day [or equivalent] followed by a taper, for grade 2 or higher pneumonitis), and/or permanent discontinuation. Monitor for signs and symptoms of pneumonitis; if pneumonitis is suspected, evaluate with radiographic imaging and administer systemic corticosteroids for grade 2 or higher pneumonitis. Pneumonitis occurred more frequently in patients with a history of prior thoracic radiation.

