Thyroid disorders: Immune-mediated hyperthyroidism, hypothyroidism, and thyroiditis have occurred. The median onset for hyperthyroidism was 1.4 months (range: 1 day to ~22 months) and the median duration was 2.1 months (range: 3 days to over 15 months). Hyperthyroidism resolved in nearly three-fourths of affected patients. Hypothyroidism occurred with a median onset of 3.5 months (range: 1 day to 19 months) and median duration was not reached (range: 2 days to over 27 months). Hypothyroidism resolved in one-fifth of affected patients. The incidence of new or worsening hypothyroidism was higher in patients with squamous cell cancer of the head and neck. Monitor for changes in thyroid function (at baseline, periodically during treatment, and as clinically indicated) and for signs/symptoms of thyroid disorders. Administer thionamides and betablockers for hyperthyroidism as appropriate; may require treatment interruption and/or permanent discontinuation. Isolated hypothyroidism may be managed with replacement therapy. Thyroiditis occurred with a median onset of 1.2 months (range 0.5 to 3.5 months).

Other immune-mediated toxicities: Other clinically relevant immune-mediated disorders have been observed (may involve any organ system or tissue, and may be severe or fatal), including rash, exfoliative dermatitis, bullous pemphigoid, uveitis, arthritis, vasculitis, myositis, Guillain-Barré syndrome, pancreatitis, hemolytic anemia, sarcoidosis, serum sickness, myasthenia gravis, myelitis, myocarditis, and encephalitis. While immune-mediated toxicity generally occurs during treatment with pembrolizumab, adverse reactions may also develop after therapy discontinuation. If an immune-mediated adverse event is suspected, evaluate appropriately to confirm or exclude other causes: withhold treatment and administer systemic corticosteroids based on severity of reaction. Upon resolution to grade 0 or 1, initiate corticosteroid taper (continue tapering over at least 1 month). When reaction remains at grade 1 or less during taper may reinitiate pembrolizumab. Immune-mediated adverse reactions that do not resolve with systemic corticosteroids may be managed with other systemic immunosuppressants (based on limited data). Discontinue permanently for severe or grade 3 immune-mediated adverse event that is recurrent or lifethreatening.

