7.5 Additional Reporting of Events to the CFCCC DSMB and Sponsor Investigator

Adverse Event/ Serious Adverse Events

Event Type	Reporting Timeframe to CFCCC DMSB (Notification is done by entering this information into OnCore within the timelines below)	Reporting Timeframe to Coordinating Center (Notification is done via email to [contact] and [contact] within the timelines below)
Serious Adverse Events (all attributions) that meet all of the following criteria: Unexpected Grades 3-5 Occurring during treatment or within 30 days of the end of treatment*	5 business days from date the PI is aware of the event	24 hours from date the site is aware of the event.
Adverse Events that meet all of the following criteria: Unexpected Study related (possibly, probably, or definitely) Grades 3-4 Occurring during treatment or within 30 days of the end of treatment*	5 business days from date the PI is aware of the event	24 hours from date the site is aware of the event.
All other Adverse Events and Serious Adverse Events should be reported as noted in the 'Recording of Events' section * Investigators are not obligated to actively seek information regarding the occurrence of recording to the accurrence of recording the	Prior to each scheduled progress review.	5 business days from the date the site is aware of the event

^{*} Investigators are not obligated to actively seek information regarding the occurrence of new AEs or SAEs beginning after the 30-day post-treatment period. However, if the investigator learns of such an event and that event is deemed relevant to the study, he/she should promptly document and report the event.

Deviations/Violations

Event Type	Reporting Timeframe to CFCCC DSMB (Notification is done by entering this information into OnCore within the timelines below)	Reporting Timeframe to Coordinating Center (Or other entity monitoring/coordinating the trial)
Violations as defined above (e.g. wrong dosage of drug administered, safety procedures not being conducted at specific time points).	5 business days from the date the PI is aware of the event	24 hours from the date the site is aware of the event

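### The protocol gives three different safety windows and no active check for new events after day 30, so late immune-mediated toxicity may be under-ascertained

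*Combined protocol and SAP*

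**What the plan says.** The combined protocol and SAP sets the safety period in three ways:

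- **Four weeks.** Section 2.3 defines the secondary endpoint as "rates of drug-related grade 3-5 adverse events experienced during and up to four weeks after completion of study treatment".
- **30 days.** Section 7.4: "Serious adverse events collection will start at the time patient signs consent until 30 days after the end of treatment". Non-serious events run from first treatment to the same end.
- **Whole participation.** Section 9.1 names a toxicity endpoint, the number of participants with serious toxicity while they take part in the trial. Section 9.2 monitors serious toxicity over the same period for the stopping boundary. Follow-up runs to death or 18 months after the last enrolment (Sections 4.7 and 5.4).

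On ascertainment, Section 7.5 states: "Investigators are not obligated to actively seek information regarding the occurrence of new AEs or SAEs beginning after the 30-day post-treatment period". Its next sentence says that an investigator who does learn of a relevant later event should document and report it promptly. The off-treatment assessment is due "Within 30 days after treatment termination". Three-monthly follow-up then consists of "Review of systems and determination of live status (either in clinic during standard visit or by phone"; the Time and Events table (Section 5.5) marks no adverse-event check in that column.

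Section 7.1.2 says of immune-mediated toxicity that "adverse reactions may also develop after therapy discontinuation".

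**The concern.** The protocol recognises new-onset immune toxicity after the last dose, yet requires nobody to look for it after day 30. Following an existing event to resolution does not help, because these events have not yet begun. The restriction in Section 4.1.2.2, "Live vaccines are prohibited while on study and until 5 months after last dose of IO" agent, also treats the immune effect as outlasting 30 days, although it is a precaution and not an estimate of event risk.

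Two results are exposed. The first is the immune-mediated safety profile, in a study where describing adverse events is an objective (Section 2.2.1) and the cited experience with this exact pair is eight renal-cancer patients (Section 1.3). The second is the Section 9.2 boundary: it says it counts serious toxicity throughout participation, but no procedure supplies the late events. A count that is too low makes the rule less likely to stop accrual.

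The 30-day period itself may also be thinly observed. An off-treatment visit on day 3 complies with Section 5.3.2, and the next scheduled contact is at about three months.

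**Working it through.** The documents give no figure for the completeness of safety collection, so there is none to reproduce. The check asks when collection closes, measured from first dose, and compares that with the onset figures in Section 7.1.2.

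**Inputs.** Onset figures: Section 7.1.2. Median PFS of 2.0 months and PFS-6 of 14.1% on pembrolizumab alone: Sections 1.1 and 1.4. Null and alternative PFS-6 of 5% and 20%: Section 9.1. Incidences: Section 7.1.4. One month = 30.44 days. *Assumption:* time on treatment equals time to progression.

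**Step 1: closing time.** Closing time = T + w, where T is median time on treatment and w is the post-treatment window.

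- T = 2.0: 2.0 + 28/30.44 = 2.92 months (endpoint); 2.0 + 30/30.44 = 2.99 months (collection).
- For a stated PFS-6 of S, an exponential curve gives T = 6 × ln 2 / (−ln S). This is 1.39 months at 5%, 2.12 at 14.1% and 2.58 at 20%. Adding 30 days (0.99 months) gives 2.37, 3.11 and 3.57 months.

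**Step 2: comparison with onset figures (months).**

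| Toxicity | Onset | After 2.37? | After 2.99? | After 3.11? | After 3.57? |
|---|---|---|---|---|---|
| Thyroiditis | 1.2 | no | no | no | no |
| Hepatitis | 1.3 | no | no | no | no |
| Hyperthyroidism | 1.4 | no | no | no | no |
| Nephritis | 3.2-5.1 | yes | yes | yes | upper figure only |
| Pneumonitis | 3.3 | yes | yes | yes | no |
| Colitis | 3.5 | yes | yes | yes | no |
| Hypothyroidism | 3.5 | yes | yes | yes | no |
| Hypophysitis | 3.7 | yes | yes | yes | yes |
| **Outside, of 8** | | 5 | 5 | 5 | 1-2 |

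**Step 3: illustrative share of events outside the window.** Assume exponential onset (rate a = ln 2 / onset median), exponential stopping (rate b = ln 2 / T), independence, and an onset rate unchanged by stopping. Then the share = exp(−a·w) × b/(a + b).

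Colitis, T = 2.0, 30 days: a = 0.198, b = 0.347, w = 0.986; exp(−0.195) × 0.347/0.545 = 0.82 × 0.64 = 0.52.

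Across the five later-onset toxicities the share is 50-54%, with nephritis at 3.2 months (63% at 5.1). With 90 days it is 32-37% (48% for nephritis at 5.1).

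**Step 4: illustrative size in 27 patients.** Take the top of the listed all-grade pembrolizumab incidences: colitis 2%, pneumonitis 3%, hepatitis 3%, and 1% each for nephritis and hypophysitis (both listed below 1%). At T = 2.0 with 30 days:

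0.02 × 0.52 + 0.03 × 0.51 + 0.03 × 0.23 + 0.01 × 0.50 + 0.01 × 0.54 = 0.043, and 0.043 × 27 ≈ 1.2 events.

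For T from 2.58 to 1.39 months the loss is 3.8 to 4.9 points, or 1.0 to 1.3 events. Adding thyroid events at their top incidences gives 13.5 to 17.4 points, or 3.6 to 4.7 events. All are all-grade figures. The grade 3-5 share is not stated, so the loss on the actual endpoint is smaller by an unknown amount.

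**The case against.** A reader might infer that collection simply ends at day 30, that most immune toxicity in a typical patient falls after it, and that the grade 3-5 rate is therefore biased downward. The documents do not support that reading.

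- Section 7.5 keeps passive reporting after day 30, and a review of systems at follow-up gives it a route. What is missing is active ascertainment.
- Five of eight depends on an assumed two months of treatment, taken from pembrolizumab alone. Under the trial's own alternative it is one or two of eight, and Section 5.6 allows treatment past progression.
- The onset medians describe affected patients of all grades, with varying and possibly longer exposure; the time origin is not stated. A 3.5-month median does not mean that a patient who stops at two months has the event after month three.
- The endpoint is defined to four weeks, and for that definition the rate is not biased. It leaves out later regimen-related events.
- Section 9.2 already promises monitoring throughout participation, so the boundary is not truncated by its own wording.
- Grade 3 or 4 events reached 68% with cabozantinib in the hepatocellular trial (Section 1.2), and Section 4.4 describes many of its events as early. A few late immune events would move the overall rate little.
- Section 7.4 requires collection to day 30 whatever the visit date.

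These points narrow the finding but do not remove it. Passive capture is weaker than asking, and a late event that is reported still falls outside Section 2.3. Participation is not defined, and if it includes follow-up, Sections 9.1 and 9.2 count events that Sections 5.4 and 7.5 do not actively collect.

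**Conclusion.** The finding holds as an inconsistency between windows and a gap in late ascertainment. Four weeks, 30 days and whole participation cannot all govern the safety count, and no scheduled procedure asks about new events after the off-treatment visit. New late immune-mediated events may be under-ascertained, and any such error is downward.

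A material bias in the overall grade 3-5 rate is not shown. The effect is probably small and cannot be computed from the documents. The illustration of about one event in 27 patients, excluding thyroid events, uses all-grade incidences at the top of their listed ranges and an assumed model. The point matters mainly for the immune-mediated profile, where one late pneumonitis or colitis in 27 patients is visible, and for the boundary count. It justifies an inexpensive amendment.

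**What to change.** Reconcile the windows in Sections 2.3, 7.4, 7.5, 9.1 and 9.2:

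1. Keep 30 days for all adverse events. Actively collect serious events, and drug-related or immune-mediated events of grade 3 or higher, to at least 90 days after the last dose of either agent, whichever is later. Include them in the safety endpoint and the boundary count.
2. Add an adverse-event check to the follow-up column of Section 5.5, with the first contact no earlier than day 90. The present ±14 days would allow about day 77 (3 × 30.44 − 14).
3. Complete the off-treatment adverse-event check at or after day 30, by phone if needed.
4. Record the start date of any new anticancer therapy, and list events that begin later separately.

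No document singles out 90 days. It uses a contact already planned, and with two months of treatment it moves closure to 2.0 + 90/30.44 = 4.96 months, past every stated onset figure except the upper one for nephritis. It does not capture everything, as Step 3 of the working shows.

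The cost is amendment wording, a phone call for some patients and a few questions at an existing contact. Some late events will be confounded by later therapy, and the reported rate may be slightly higher.

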7.5 Additional Reporting of Events to the CFCCC DSMB and Sponsor Investigator

Adverse Event/ Serious Adverse Events

Event Type	Reporting Timeframe to CFCCC DMSB (Notification is done by entering this information into OnCore within the timelines below)	Reporting Timeframe to Coordinating Center (Notification is done via email to [contact] and [contact] within the timelines below)
Serious Adverse Events (all attributions) that meet all of the following criteria: Unexpected Grades 3-5 Occurring during treatment or within 30 days of the end of treatment*	5 business days from date the PI is aware of the event	24 hours from date the site is aware of the event.
Adverse Events that meet all of the following criteria: Unexpected Study related (possibly, probably, or definitely) Grades 3-4 Occurring during treatment or within 30 days of the end of treatment*	5 business days from date the PI is aware of the event	24 hours from date the site is aware of the event.
All other Adverse Events and Serious Adverse Events should be reported as noted in the 'Recording of Events' section * Investigators are not obligated to actively seek information regarding the occurrence of recording to the accurrence of recording the	Prior to each scheduled progress review.	5 business days from the date the site is aware of the event

^{*} Investigators are not obligated to actively seek information regarding the occurrence of new AEs or SAEs beginning after the 30-day post-treatment period. However, if the investigator learns of such an event and that event is deemed relevant to the study, he/she should promptly document and report the event.

Deviations/Violations

Event Type	Reporting Timeframe to CFCCC DSMB (Notification is done by entering this information into OnCore within the timelines below)	Reporting Timeframe to Coordinating Center (Or other entity monitoring/coordinating the trial)
Violations as defined above (e.g. wrong dosage of drug administered, safety procedures not being conducted at specific time points).	5 business days from the date the PI is aware of the event	24 hours from the date the site is aware of the event
 Deviations as defined above, including: Planned deviations (e.g. rescheduling a visit that will be out of window due to a holiday) Unplanned deviations (e.g. rescheduled visit, a missed routine safety laboratory test for a participant with previously normal values) 	Prior to each scheduled progress review	5 business days from the date the site is aware of the event

